#### Part A- Perception of self-paced performance variations (2 hour and 30 minutes)

## Part B- Perception of imposed performance variations (1 hour and 40 minutes)

[figure not shown]

Figure 3 Experimental outline of the study. \*Note that Clinical assessment + Familiarization and Part A can be also on the same day. VAS-F= Visual analogic scale for fatigue, COP= Center of pressure

## Clinical assessment + familiarization

- **Clinical assessment**

The participants will be contacted to verify their interest and eligibility (inclusion and exclusion criteria) to participate in the study. In the case of inclusion in the study, demographic data will be recorded via web-based secured digital surveys (Castor® web application) and filled in by the examiner, including: 'Sex', 'Age', 'Body Mass Index', 'Work status', 'Year from diagnosis' (if living with a chronic condition, specifying the subtype when relevant), 'Use of assistive device for walking in daily life', 'Use of medications' (that could influence fatigue, motor or cognitive performance).

### -Questionnaires

Different questionnaires will be handed-out to the participants or, when the online filling modality is preferred by the participant, they will be sent to them in via a secured web link (available via Castor®). We will ask the participant to make this choice when they will be informed about their eligibility in the study.

Part of the questionnaires will serve as screening tools for factors that potentially interfere with the perceptive abilities of the participants: The Godin Leisure-Time Exercise questionnaire (GLTEQ) for the level of physical activity; the Pittsburgh Sleep Quality Index (PSQI) for sleep quality in the last month; the General Self-Efficacy scale (GSE) for self-efficacy beliefs; the Checklist for Symptoms in Daily life (CSD) for self-reported habitual symptom perception; the Brief Pain Inventory (BPI) to measure the severity of pain and its impact on daily functioning; the Falls Efficacy Scale International (FES-I) for the level of concern about falling; the Hospital Anxiety and Depression Scale (HADS) for screening the presence of symptoms of anxiety or depression in the last week; the Positive and Negative Affect Schedule (PANAS-SF) to assess positive and negative affectivity; the Fatigue Scale for Motor and Cognitive Functions (FSMC) for fatigue; the Modified Fatigue Impact Scale (MFIS) for

perceived impact of fatigue; and, only for PwMS, the Control subscale of the Multiple Sclerosis Self-Efficacy scale (MSSE-c) for disease specific control beliefs and the Multiple Sclerosis Walking Scales (MSWS-12) for perceived walking ability.

To investigate the participant's subjective beliefs about their perceptive abilities and compare the ones of PwMS to the ones of HC, the Multidimensional Assessment of Interoceptive Awareness (MAIA-2) and the Interoceptive Sensitivity and Attention Questionnaire (ISAQ), that register self-beliefs over interoceptive abilities and the Postural Awareness Scale (PAS), measuring self-beliefs over proprioceptive abilities, will be administered to both groups.

---

### **Research questions relative to the reported subjective beliefs about perceptive abilities**

- Do PwMS and HC differ in their reported subjective beliefs about perceptive abilities quantified by the MAIA-2, ISAQ and PAS scores and subscores?

### **Hypothesis**

- PwMS differ from HC in their reported subjective beliefs about perceptive abilities: lower interoceptive and postural awareness (MAIA-2 and PAS total score) and higher attention and sensibility (ISAQ total score) is expected in PwMS

### **-Cognitive and motor performance assessments**

For the execution of the cognitive and motor performance tests, participants will be asked to reach the clinic (MS Rehabilitation Center – Noorderhart, Pelt or National MS Center, Melsbroek), or, in case is more convenient for the participants the REVAL research center, to meet the experimenter. A short briefing will serve to ask the participants if they had difficulties in filling the surveys online and check for mistakes or missing answers. Participants will be also asked to wear flat comfortable shoes (mandatory characteristics of shoe's sole: maximal difference between heel and toes sole height= 1 cm) and to carry with them shorts or legging pants for a better fixation of the sensors; they will be required to wear the same clothing for all the different parts of the study.

Participants will be tested for cognitive executive functions (ie. information processing speed) via the Symbol Digit Modalities Test (SDMT) if they are not able to provide the result of a recent (<6 months) SDMT. In case the patient is contacted in the MS centers, the clinics will provide the result of the most recently executed SDMT. The SDMT is a timed thinking task that involves associating numbers with symbols. Participants will be asked to provide as many correct numbers as they can within 90 seconds.

Visuospatial memory will be assessed with the Revised Brief Visuospatial Memory Test (BVMT-R). The BVMT-R is a visuospatial memory test, such that participants view a stimulus page for 10 seconds and are asked to draw as many of the figures as possible in their correct location on a separate sheet of paper.

Participants will be instructed to walk as fast as possible to measure their maximal walking speed with the Timed 25-Foot Walk test (T25-FW). The test will be performed with a flying start, it will be repeated two times and the average time of the two trials be used as the final performance.

The Test for the Sensory Interaction of Balance will be used to define the proprioceptive interaction on balance: force plates will measure center of pressure (COP) displacement in response to standing

on a stable and unstable support surface (standard foam pad), with eyes open and closed. The degree of increase in COP displacement when applying the foam represent the proprioception quotient (i.e. reliance of body balance on the proprioceptive system). (23)

After each of the four conditions of the Test for the Sensory Interaction of Balance the participant will be asked for a Rate of Perceived Stability, a 1-10 visual analogical scale to rate balance challenge.(24)

#### 6.4 Rate of Perceived Stability \*

Afterwards, the participants will perform the 6 Minute Walk Test (6MWT), walking back and forth in a 30m corridor as fast and safe as possible for 6 minutes, the 30 seconds Chair Stand Test (30CST), repeating STS transitions as fast and safe as possible for 30 seconds, and the Dual Joint Position Test (DJPT), a test for proprioception. (25)

Except for the T25FW, the participant will wear wearable sensors in pre-defined body positions for the gait and STS tests (6 OPALs – APDM technology© IMU sensors: 2 over the dorsal part of the feet, 2 on the lower legs, 1 anterior to the sternum and 1 posterior to the third/fourth lumbar vertebra; 1 Polar H10 chest-band for real-time heart rate monitor).

Figure 4 Wearable sensors placement on the body and working prototype of the force sensing device for perceptive tasks

The perceived fatigue will be asked just before and immediately after the 6MWT and the 30CST using the VAS-F, a 0-10 visual analogical scale for state fatigue.

Figure 5 10 points visual analogic scale for fatigue (VAS-F)

- **Familiarization with motor and perceptive tasks**

At this point the participant will be familiarized with the experimental procedures and the experimenter is defining the ranges of performance variations that will be experimentally-induced in part B. This will happen in the presented order:

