# Assessment of perceptive accuracy for motor performance in persons with multiple sclerosis

## Introduction

The majority of people with multiple sclerosis (PwMS) have impaired gait and sit-to-stand function: they walk slower, with an increased energetic cost of walking and cluster-specific alterations from the physiological gait pattern, while lower limb extensor weakness and diminished postural control have also an impact on their sit-to-stand performance. (1-4)

After sustained activity these impairments tend to increase for a large part of PwMS: motor performance fatigability, the objectively measured acute performance deterioration, may involve both quantitative and qualitative aspects of their motor performance. (5, 6)

This can be a barrier to participation in leisure-time physical activity (PA), creating a vicious circle leading to increase in disability: inactive PwMS walk slower with an increased energetic cost of walking, consequently experiencing more reductions in walking bouts quality and distance in their daily life.

Furthermore, motor performance impairments and levels of PA, in this population, may also be linked to sensory abnormalities, personal beliefs and fluctuations of symptom intensity. (7-11)

Fatigue is the hallmark symptom in MS, with reported prevalence reaching 78%, and PwMS with higher levels of perceived fatigue tend to become less physically active in their daily life, also in absence of motor performance fatigability. (12, 13)

Generally, fatigue is a sense of tiredness and lack of energy that can interfere with a person's usual daily activities and, leading to increase the weighting of effort costs in cost-benefit evaluations, it can be a functional interoceptive signal to stop or modify our activity, take appropriate rests or pace our efforts. (14)

[figure not shown]

Figure 1 The predictive model of bodily states. Illustration of the interoceptive core control network and of the precision weighted inferential process forming perception. Adapted from (15)

The efficiency of this self-regulation system depends on the ability of the central interoceptive core control network to accurately judge our body state (which resources are available versus necessary to achieve a desired outcome) and, when carrying out physical activity, to timely produce allostasis adjustments (i.e. 'actions to maintain the body in homeostasis') through interactions with the

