## **Experimental design Part B: 'Perception of imposed performance variations'**

### **Task 1: Perceptive accuracy for imposed speed variations during treadmill walking**

On the third day the participants will be tested on the treadmill starting from a familiarization with the range of treadmill speed, personalized accordingly to a subjective and an objective criteria (see above, 'Range of experimentally-induced performance variations – Treadmill walking'). Consequently, the treadmill speed will be quickly returned to comfortable.

Neutral instructions will be provided to the subject before starting the treadmill test by reading the following script: "Start walking when the treadmill moves and try to pay attention to the belt speed, starting at your comfortable level. You should try to maintain your position on the treadmill for the full length of the experiment. Use the lateral bars for hand support in case of brief necessity but release them as soon as you can. We want you to notice, evaluate and report the actual treadmill speed to the experimenter relative to the visual scale on the screen: its starting position on the zero value of the scale represent your comfortable walking speed. Variations in belt speed may occur at any point throughout the experiment, always within your personalized range of speed. Sometimes it is possible that you will not feel any belt speed variation at all. Every 10 seconds you will be asked to communicate the speed level you are perceiving at that point in time, and your report will be recorded".

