In the **experimental Part B** within-subject correlations will be calculated between the imposed performance in motor tasks and the perception of its variations. These correlations will be examined separately for different phases of each trial to index perceptive accuracy. Fisher Z transformations (or other types of transformations eg. log transformation) will be applied to these correlations before further analysis, with results back-transformed for reporting. We will study it between and within groups using a mixed model ANOVA with time (protocol subphase) and group as factors to detect significant differences between PwMS and controls and its variations relative to the different subphases of the protocol. To investigate its interference with perceptive accuracy the difference between the subjective rate of fatigue (VAS-F) pre-post protocols will be included in the analysis as covariate. The correspondence between measured and reported dimensions of perceptive accuracy will be calculated as their absolute difference and compared between groups using an independent T test (or with its non-parametric equivalent).

Finally, for the accuracy outcomes derived from both experimental parts we will explore correlations, separated per group, to investigate the relationship between objectively measured perceptive accuracy and factors that potentially interfere with it (demographics, questionnaires and clinical assessments). Then, a regression analysis will be performed to assess the strength of these relationships and identify the most important explanatory factors or predictors.

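### As listed, the proprioception test (DJPT) follows two as-fast-as-possible exercise tests with no stated rest, so its scores may partly reflect acute fatigability

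*Combined protocol and SAP*

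**What the plan says.** The section on cognitive and motor performance assessments goes through the SDMT, the BVMT-R, the T25-FW and the Test for the Sensory Interaction of Balance with its perceived-stability rating. It then continues: "Afterwards, the participants will perform the 6 Minute Walk Test (6MWT"), which is described as "walking back and forth in a 30m corridor as fast and safe as possible for 6 minutes". Next comes the 30CST, "repeating STS transitions as fast and safe as possible for 30 seconds", "and the Dual Joint Position Test (DJPT), a test for proprioception". Perceived fatigue (VAS-F) is recorded before and after the 6MWT and the 30CST. No VAS-F is stated at the DJPT, and no rest interval or recovery criterion is written.

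On exertion, the Introduction says: "After sustained activity these impairments tend to increase for a large part of PwMS". The impairments meant are those of gait and sit-to-stand. The Participants section asks people to avoid unusual physical activity for at least 24 hours before data collection.

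On use of the result, the section on data and statistical analysis compares clinical assessment outcomes between groups with a t test or Mann-Whitney test. It then relates perceptive accuracy, within each group, to "factors that potentially interfere with it (demographics, questionnaires and clinical assessments"), followed by a regression to find the main explanatory factors. The DJPT is not named there, but it is one of the clinical assessments.

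**The concern.** A proprioception score is most useful here as a description of the participant that may explain how well he or she perceives motor performance. Taken after six minutes of fast walking and 30 seconds of fast chair stands, it may also carry a short-lived effect of that exertion.

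Two analyses could be blurred. In the group comparison, a PwMS-control difference could be partly a difference in response to the preceding tests. In the explanatory analyses, the hypotheses for Parts A and B expect lower accuracy in PwMS with higher reported fatigue. If the DJPT partly reflects fatigability, an association between DJPT and accuracy is hard to tell apart from that fatigue hypothesis.

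The other proprioceptive measure, the foam-based balance quotient, is listed before the 6MWT. As written, the two proprioceptive measures are taken in different states, although an earlier slot for the DJPT is available.

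**Working it through.** **Order of tests.** The sequence as listed is balance test, 6MWT, 30CST, DJPT. The word that opens the sentence places all three later tests after the balance test. Within the sentence the order follows only from the listing. The explicit statement that steps run in the order presented applies to the familiarization that follows, not to this list. Figure 3, the study outline, is not reproduced in the text available, so an order or a rest period shown there cannot be excluded.

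**What the documents give on size.** They give no effect of exercise on the DJPT, no SD and no comparison with controls. The Introduction's statement is qualitative and concerns gait and sit-to-stand. Any magnitude is therefore an assumption.

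**Illustration for the group comparison.** Inputs from the documents: 40 per group (44 recruited, 40 plus 10%) and α = 0.05. Assumptions: two-sided test, normal scores with equal SD, no true group difference in proprioception, and an excess exercise shift of d SD in PwMS over controls.

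- Noncentrality: δ = d × √(n/2) = d × √20 = 4.472 × d.
- Degrees of freedom: 2 × 40 − 2 = 78, with critical value 1.991.
- Rejection rate: P(|T| > 1.991), where T is noncentral t with 78 degrees of freedom and noncentrality δ.

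| Assumed excess shift d (SD) | δ | Rejection rate |
|---|---|---|
| 0 | 0 | 5% |
| 0.1 | 0.447 | 7% |
| 0.2 | 0.894 | 14% |
| 0.3 | 1.342 | 26% |
| 0.5 | 2.236 | 60% |

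A normal approximation gives 7%, 15%, 27% and 61% for the four non-zero shifts, so the choice of method hardly matters. The table shows how sensitive the comparison would be. It does not estimate what will happen in this study.

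**Explanatory analyses.** The correlations are run separately per group. A shift common to all PwMS would leave the within-group correlation unchanged. Distortion needs an exercise effect that differs from person to person and also tracks accuracy. That is possible, since fatigability varies among PwMS, but the documents give nothing from which to quantify it.

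**The case against.** The strongest reply is that this is peripheral. The DJPT appears in no research question or hypothesis, and the particular focus of the clinical comparisons is on the MAIA-2, ISAQ and PAS. The correlations are exploratory. The protocol never calls the DJPT a resting or trait measure, and PwMS must be able to walk six minutes without rest or aid. A second proprioceptive measure is listed before the exertion, and the VAS-F after the 30CST gives some handle on acute fatigue. All of this stands and limits the weight of the point. It does not remove it, because the later VAS-F is not stated to coincide with the DJPT, and the balance quotient is a different test.

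A reader might go further and infer that exercise effects on the DJPT are larger in PwMS than in controls. The documents do not support this, since the cited statement neither mentions proprioception nor compares with controls.

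A reader might also infer that the zero of the Part B treadmill scale is biased. The comfortable speed is chosen after the same tests and 10 minutes of treadmill walking, when "the experimenter is defining the ranges of performance variations that will be experimentally-induced in part B", and it is the start of the task in Part B. This does not hold as a criticism of the planned analysis, for three reasons:

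- The Part B outcome is a within-subject correlation between perceived and actual speed, and adding a constant to either variable leaves a correlation unchanged.
- The imposed change is 15 × 0.028 = 0.42 m/s, capped at the participant's maximal speed. A comfortable speed lowered by fatigue would widen the room below that cap, not narrow it.
- The selection starts from 50% of a speed derived from the 6MWT, so on day 1 it has to follow that test.

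**Conclusion.** The point holds in a limited form and is minor. As listed, the DJPT comes after two tests done as fast as is safe, with no rest stated in the readable text, and its scores may partly reflect acute fatigability. The analyses exposed are the exploratory group comparison of the DJPT and its use as an explanatory factor.

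The size is unknown. The rejection rates of 14%, 26% and 60% depend wholly on the assumed excess shifts of 0.2, 0.3 and 0.5 SD in PwMS, with no true difference and 40 evaluable per group. The conclusion also assumes that the listed order is the order performed and that Figure 3 shows no rest period. No planned Part B outcome is shown to be affected.

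**What to change.** Perform the DJPT alongside the Test for the Sensory Interaction of Balance, before the 6MWT and 30CST, and write that order into the protocol. It would still follow the T25-FW, but that is two 25-foot walks and not sustained activity. The cost is nil: the same tests in the same session, in a different order.

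If the present order must stay for practical reasons, state the rest given before the DJPT, record a VAS-F at that point, and examine it when the DJPT is analysed. This adds one rating and any rest time, and is weaker than changing the order.

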**Familiarization with perceptive task for Part A – ‘Perception of self-paced performance variations’**

A perception reporting familiarization procedure will ensure that the participants understand the instruments and methods utilized by the experimenter to register their subjective reports on their ongoing motor performance. The participant will be equipped with noise-cancelling headphones and an hand-held force sensing device, shaped in a similar fashion as the Jamar hand-dynamometer®: instructors will explain that the device will be utilized during motor tasks like walking and sit to stand for recording the time-point of any perceived changes in their own motor performance (in 'gait speed or smoothness' during a 6MWT or in 'sit-to-stand duration or smoothness' during repeated STS postural transitions). The threshold sensitivity of the sensor (ie. the minimum value of input hand-grip force to save a report) will be set at 25% of the maximal hand-grip strength of the participant (average of three maximal isometric hand-grip test, measured with the same sensor). Trials are executed with the use of simple perception tasks (eg. reacting to visual stimuli while walking or doing STS repetitions) and the participant is informed that he will be following these same instructions to report his own perception about unspecified aspects of their motor performance during walking and STS in the experimental Part A of the study.

#### **Range of imposed performance variations (part B) – Treadmill walking**

A treadmill familiarization procedure will ensure that every participant is enrollable to perform experimental part B. The subjects will be asked about previous experiences with treadmill training/use and this will be noted down in the participant file: participants will undergo 10 minutes of treadmill walking with the supervision of a physiotherapist to familiarize with the moving belt, position and use of safety bars and other general safety and usability issues.

A speed-range definition procedure will permit the quantification of the appropriate personalized range of experimentally-induced performance variations for every participant. All the participants will start walking on the treadmill at 50% of their *maximal treadmill walking speed* (speed calculated from their overground performance in 6MWT: maximal speed maintained for at least 15 seconds during the test) and they will be asked to confirm if that is their *comfortable treadmill walking speed*; if this is not the case the experimenter will adjust the speed based on the participant's subjective reports and, finally, will let them walking at that constant speed for one minute.

Immediately after the selection of their *comfortable treadmill walking speed* (i.e. during the one minute of constant speed walking) the participants will be instructed to maintain their position on the treadmill, in the antero-posterior direction, adapting their gait to the belt continuous acceleration toward their maximal walking speed (selected from their overground performance in 6MWT, see paragraph above). This speed range, will be used as personalized range of experimentally-induced performance variations (in Part B).

